### 2.5.2. ASSESSMENT TIMELINES/SCHEDULE

Clinical and Radiographic Exams						
Data Collection item	Pre-operative	Intra-operative	Immediate Post-operative	6 Months	1 Year	2 years
Demographic and Medical History	X					
Operative Record		X				
Clinical Evaluation – OHS, HHS	X			X	X	X
Radiographic assessment			X	X	X	X
Squeaking, Dislocation			X	X	X	X
Adverse events including revisions			As required			

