### 3.4. Subject withdrawal

Subjects may be withdrawn from the trial at any time for any of the following reasons:

- At subject's own request
- Death of subject
- Failure to return for follow-up
- Removed from evaluation – a written explanation by the investigator is required.

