#### 3.3.1 Early Termination of Clinical Investigation

The clinical investigation can be discontinued at the discretion of the Chief Investigator or of Sponsor in the case of any of the following:

- Inefficacy of the study device.
- Occurrence of adverse events unknown to date with respect to their nature, severity and duration or the occurrence of known adverse events with unexpected frequency.
- Acquisition of new scientific knowledge during the conduct of the study which shows that the sense or ethical claim of the study is no longer valid.

If the subject is withdrawn for any reason at any time a final evaluation form will be completed and the Sponsor will be notified.

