## 5. ADVERSE EVENT MANAGEMENT AND REPORTING

A record of all adverse events, including details of the nature, onset, duration, severity, relationship to the device, relationship to the operative procedure and outcome, will be made and provide to the Sponsor. The subject will be questioned about any adverse event(s) at each subsequent follow-up assessment visit. Serious Adverse Events that are related to the device should be reported to the Ethical Committee and Sponsor as soon as possible. These include any untoward medical occurrences that result in death, are life threatening, require in patient hospitalization, or prolongation of existing hospitalization, result in persistent or significant disability/incapacity, or resulted in a congenital anomaly/birth defect.

***“Any general adverse events that are not related to hip, will be reported once symptomatic diseases are administered and confirmed by other departments.”***

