### 6.2 HANDLING OF MISSING AND INCOMPLETE DATA

Attempt will be made to ensure that patients come back for scheduled follow-up evaluations. In case of missing data, for clinical outcome scores, Last Observation Carried Forward will be used to impute the missing data. For survivorship analysis, the data including implant in situ collected in the next follow-up will be used to calculate survivorship

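### The only survivorship rule depends on a next follow-up: taken literally it can back-date a failure, and it gives no value for hips with no later visit

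*Combined protocol and SAP*

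**What the plan says.** Sections 2.4 and 6.3 list survivorship among the secondary endpoints without defining it. The one sentence on its calculation is in section 6.2, under "HANDLING OF MISSING AND INCOMPLETE DATA". That section first deals with the scores, "In case of missing data, for clinical outcome scores, Last Observation Carried Forward will be used to impute the missing data", and then adds: "For survivorship analysis, the data including implant in situ collected in the next follow-up will be used to calculate survivorship".

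Three other places bear on what is known about a revised hip:

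- The schedule in section 2.5.2 has a row for "Adverse events including revisions", collected as required and not tied to a visit.
- Section 5 calls for "A record of all adverse events, including details of the nature, onset, duration, severity, relationship to the device" and further details, to be given to the sponsor.
- Section 3.3.1 states: "If the subject is withdrawn for any reason at any time a final evaluation form will be completed and the Sponsor will be notified".

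The withdrawal reasons in section 3.4 include the subject's request, death, "Failure to return for follow-up" and "Removed from evaluation – a written explanation by the investigator is required". Section 6.1 allows for 15% dropout or loss to follow-up.

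No section defines the survivorship event, its date, a censoring rule or an estimator. No section says that adverse event dates or the final evaluation form feed the survivorship analysis.

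**The concern.** A rule that looks forward to the next visit has two weaknesses for a time-to-event endpoint. First, status at a later visit need not be the status at the missed one, because the revision may fall between the two. Second, the rule needs a later visit to exist. It gives nothing for a hip whose patient has left, or for anyone who misses the 2-year visit, since nothing is scheduled after that.

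The second weakness matters more if leaving is related to implant failure, which is plausible though not stated in the plan. Implant survival bears directly on the trial's stated purpose of evaluating the safety and effectiveness of the two cups. Events are likely to be few in an arm of 80, so omitting or misplacing one or two would visibly change the reported figure.

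**Working it through.** **The plan's own figures.** The documents give no number for survivorship. The sample size in section 6.1 supplies the arm size and the expected loss, and it reproduces:

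- n per group = 2 × (1.960 + 0.842)² × 12² / 5.8² = 67.2, rounded up to 68.
- 68 / (1 − 0.15) = 80 per group, so the plan expects 80 − 68 = 12 hips per arm to be lost.

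**The rule applied to three kinds of hip.**

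| Hip | Status under section 6.2 taken literally | Other records the plan calls for |
|---|---|---|
| Misses 1 year, revised at 18 months, attends 2 years | Not in situ at 2 years, so 1 year is filled as a failure although the cup was in place then | Adverse event record with onset |
| Revised at 3 months, then withdrawn | No next follow-up, so no status | Adverse event record; final evaluation form |
| Misses 2 years, is lost, or dies | No later visit, so no status | Final evaluation form, if counted as withdrawn |

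In the first row, one back-filled failure among 80 hips moves 1-year survival from 100% to 79/80 = 98.75%, an understatement of 1.25 points. In the second row, omitting a revision moves survival upward.

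**Size of omission, with assumed events.** Assume 80 hips in an arm and 4 revisions, at months 2, 4, 9 and 18. The range below comes from two denominators: dropping only the lost revised hips, or also dropping 10 unrevised hips that left.

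| Revisions lost | Only revised hips dropped | 10 unrevised leavers dropped too |
|---|---|---|
| 0 (all counted, all 80 hips) | 4/80 = 5.0% | – |
| 1 | 3/79 = 3.8% | 3/69 = 4.3% |
| 2 | 2/78 = 2.6% | 2/68 = 2.9% |

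With only the revised hips dropped, each lost revision lowers apparent failure by about 1.2 points (5.0 − 3.8 = 1.2; 5.0 − 2.6 = 2.4 for two).

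**Kaplan-Meier on the same assumptions.** All four revisions enter at their own dates, and the 10 unrevised leavers are censored evenly over 24 months. The expected number at risk at time t is 80 − earlier revisions − 10t/24:

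- Month 2: 79.17; month 4: 77.33; month 9: 74.25; month 18: 69.50.
- Survival = (1 − 1/79.17)(1 − 1/77.33)(1 − 1/74.25)(1 − 1/69.50) = 0.9476, so failure is 5.2%.

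Over 5,000 simulated uniform censoring patterns, the mean was 5.24% (range 5.05% to 5.50%).

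**The case against.** The strongest reply is that the sentence is a missing-data rule and not a general rule for dating revisions. On its natural reading, it fills a missed visit from the next attended one. It also speaks of data including implant status, so it is not confined to a yes/no answer. Revisions are collected as adverse events with onset, so the patient revised at 18 months should have that date on record. A revision already recorded is arguably not missing at all. Section 3.3.1 requires a final evaluation form at any withdrawal. The paragraph on primary and secondary endpoint analysis keeps any case with complete data on at least one endpoint and states intention to treat. Revision is not itself a listed reason for withdrawal, so a hip that is revised and then leaves is an assumed pathway.

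Most of this stands, and it limits the conclusion. A reader might infer that the plan will misdate revisions, or that a revised hip whose patient withdraws necessarily drops out. The documents do not support either: nothing tells the analyst to discard a recorded revision date or delete such a hip. A reader might also infer that the rule always flatters survival. It does not, because the back-filled failure works the other way at 1 year.

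The reply does not close the gap. Limiting the rule to missing data does not help the missed 1-year visit, which is exactly the case it covers. Collecting a date is not the same as using it: section 6.2 names a later visit as the source and no section names another. The content of the final evaluation form is not described, so implant status may or may not be on it. Membership of the analysis population does not say how a hip enters the survivorship calculation.

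**Conclusion.** The point holds as a defect in the stated method, with conditional consequences. The single survivorship rule can put a failure at 1 year that occurred later, and it is silent on every hip with no later visit. Whether a revision is lost or misplaced in practice depends on whether the analyst goes beyond section 6.2 to the adverse event records and the final evaluation form.

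The direction of bias is mixed. The size is illustrative only: the 4 revisions, their timing, the number lost and the 10 unrevised leavers are all assumptions. On those assumptions, losing one or two revisions takes 2-year failure from 5.0% crude (about 5.2% by Kaplan-Meier) to 3.8–4.3% or 2.6–2.9%.

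This is a secondary endpoint with no stated test or power target, and the primary endpoint and the sample size are untouched. The change should be made because it is cheap and the endpoint bears on device safety.

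**What to change.** Replace the survivorship sentence in section 6.2 with text along these lines:

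> Survivorship is the time from index surgery to the actual date of revision, taken from the operative or adverse event record whether or not the patient attends a later visit or has been withdrawn. Unrevised hips are censored at the last date on which the implant is known to be in situ (visit, final evaluation form or adverse event contact), or at death. Kaplan-Meier estimates with 95% confidence intervals will be reported by randomised arm at 1 and 2 years.

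Record on the final evaluation form whether the implant is in situ and, if not, the date of revision.

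The cost is one paragraph and one item on a form that the protocol already requires. Surgery date and adverse event onset are already collected, and no extra patients or visits are needed.

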### 6.3 DATA ANALYSES

The following analyses will be performed:

Primary endpoint is Harris Hip Score (HHS) at 1 year follow-up.

Secondary endpoints include

- Harris Hip Score at 2 years postop
- Oxford Hip Score at 6 months, 1 and 2 years postop
- Radiographic Assessment at Immediate post-op, 6 months, 1 and 2 years postop
- Incidence of squeaking at different follow-up visits
- Dislocation rate at different follow-up visits
- Survivorship

# Clinical Research Protocol

## Primary and Secondary Endpoint Analysis

Analysis for primary and secondary endpoints will use patient population which consists of those cases with complete data for one or more of the primary and secondary endpoints. Analysis is based on intention to treat principle.

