# Clinical Research Protocol

## 6. STATISTICAL ANALYSIS PLAN

### 6.1 SAMPLE SIZE CALCULATION

This is a multi-center, randomized controlled study to compare G7 Acetabular System /CoC articulation/Taperloc Complete Microplasty stem with Exceed ABT Acetabular System /CoC articulation/Taperloc Complete Microplasty stem. The primary endpoint is Harris Hip Score at 1 year postop. Study sample size is determined assuming the use of an independent, two-sided, two-sample pooled t-test for differences in mean Harris Hip Score.

Assumptions:

$\alpha = 0.05$	Probability of Type I Error
$\beta = 0.20$	Probability of Type II Error
$sd = 12$	Estimated standard deviation of the differences based on current Exceed ABT CoC study in Korea

Based on the assumptions above, a mean difference in Harris Hip Score of 5.8 points between groups can be detected with 68 cases in each group. If 15% dropout/lost to follow-up is assumed this will give n=80 in each group.

A total of 160 cases will be enrolled in the study.

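### The set called intention to treat requires post-operative endpoint data, and with unrestricted LOCF it lets a pre-operative Harris Hip Score stand as the 1-year primary outcome

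*Combined protocol and SAP*

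**What the plan says.** The only definition of who is analysed is under Primary and Secondary Endpoint Analysis, at the end of section 6. The population is "those cases with complete data for one or more of the primary and secondary endpoints", followed by "Analysis is based on intention to treat principle". No modified intention-to-treat, per-protocol or sensitivity set is defined.

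Section 6.3 states "Primary endpoint is Harris Hip Score (HHS) at 1 year follow-up". The secondary endpoints include "Radiographic Assessment at Immediate post-op, 6 months, 1 and 2 years postop", along with squeaking, dislocation, survivorship and later scores.

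For missing clinical scores, section 6.2 states "Last Observation Carried Forward will be used to impute the missing data". It does not say which earlier observations may be carried, or how far.

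In the schedule (2.5.2), the row "Clinical Evaluation – OHS, HHS" is marked pre-operatively and at 6 months, 1 year and 2 years. Radiographs, squeaking and dislocation are also recorded immediately after surgery. Section 2.5.3 times the follow-up visits from surgery.

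Section 6.1 sizes the trial on a "two-sided, two-sample pooled t-test for differences in mean Harris Hip Score" with 68 per group, then adds: "If 15% dropout/lost to follow-up is assumed this will give n=80 in each group".

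**The concern.** Two problems follow from reading these sections together.

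First, entry to the set depends on data obtained after randomisation. A patient who is randomised but not operated on has no post-operative endpoint and no visit dates, so drops out of a set that is said to follow intention to treat. The same holds for a patient who is operated on but never assessed.

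Second, the threshold for entry is very low. One immediate post-operative radiograph qualifies a patient for the analysis of every endpoint, including 1-year HHS. If that patient is lost before 6 months, the only HHS on file is pre-operative. LOCF as written then enters a score from the diseased, unoperated hip as the result of the arthroplasty one year later. This dilutes any real difference and inflates the variance. If it happens more often in one arm, it also shifts the comparison.

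**Working it through.** **1. The plan's own figures.** Inputs from section 6.1: α = 0.05 two-sided, power 0.80, SD 12, difference 5.8.

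n per group = 2 × (1.960 + 0.842)² × 12² / 5.8² = 67.2, rounded up to 68. The exact noncentral t gives 79.9% power at 68 (69 is the first size to reach 80%), which is within rounding. Allowance for loss: 68 / 0.85 = 80 per group, 160 in total. The stated sizes reproduce.

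**2. What LOCF does case by case.**

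| Patient | In the set? | 1-year HHS analysed |
|---|---|---|
| Randomised, not operated on or never assessed | No | None |
| Immediate post-operative radiograph, lost before 6 months | Yes | Pre-operative HHS |
| Seen at 6 months, missing at 1 year | Yes | 6-month HHS |
| Seen at 1 year | Yes | Observed |

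**3. Effect of baseline carry-forward on power.** Assumptions, none in the documents: a proportion p of each arm is carried from baseline; pre-operative HHS is G = 30 to 40 points below the 1-year level; carried scores show no treatment effect; SD is 12 within both carried and observed scores.

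- Expected difference = 5.8 × (1 − p)
- SD = √(12² + p(1 − p)G²)
- Noncentrality = difference / (SD × √(2/80)), with 158 degrees of freedom and critical value 1.975

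For p = 5% (4 of 80 per arm), the difference is 5.8 × 0.95 = 5.51.

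- G = 30: SD = √(144 + 0.0475 × 900) = 13.67; noncentrality 2.55; power 71.7%.
- G = 40: SD = √(144 + 0.0475 × 1600) = 14.83; noncentrality 2.35; power 64.6%.

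| p carried from baseline | Difference | SD (G = 30, 40) | Power (G = 30, 40) |
|---|---|---|---|
| 0% | 5.80 | 12.0 | 86.0% |
| 2.5% | 5.66 | 12.9, 13.5 | 78.8%, 74.8% |
| 5% | 5.51 | 13.7, 14.8 | 71.7%, 64.6% |
| 15% | 4.93 | 16.1, 18.7 | 48.7%, 38.3% |

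The last row is the extreme in which all of the plan's 15% loss falls before 6 months. For comparison, leaving the same patients unimputed costs far less: 84.1% power with 76 observed per arm (5% missing) and 79.9% with 68 (15% missing). The imputation rule, rather than the loss itself, does most of the damage.

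**4. Shift between arms.** With no true difference and equal carry-forward in both arms, the expected shift is p × G − p × G = 0. Each percentage point by which the proportions differ moves the estimate by 0.01 × 30 to 0.01 × 40 = 0.3 to 0.4 points.

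**5. Effect of the exclusion alone.** Suppose 2.5% of one arm (2 of 80) and none of the other have no endpoint data, and those patients would have scored 5 to 20 points lower. Bias = 0.025 × 5 to 0.025 × 20, about 0.1 to 0.5 points, and two-sided type I error is about 5.1% to 5.8%. Equal exclusion with the same deficit in both arms gives no bias.

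**The case against.** The sentences can be read together. Anyone with at least one endpoint is included, patients are analysed in the arm assigned, and LOCF supplies a missing score. On this reading LOCF is the way a patient without a 1-year HHS enters the primary analysis, and almost every operated patient is kept. That stands: the rules are not mutually exclusive, and the exclusions are probably few.

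A reader might go further and infer a complete-case analysis: 68 per arm instead of 80, membership in doubt for 24 of 160 patients (15%), and type I error of roughly 8–16% if loss were 10% against 20% with lost patients 10 to 20 points worse. The documents do not support this. The condition is complete data for one or more endpoints, not for 1-year HHS, so a patient operated on, assessed and later lost stays in. The 68 in section 6.1 is the usual allowance for dropout and defines no analysis set. The 8–16% describes an analysis that the plan does not specify. Nor can differential loss be inferred from an unmasked design: the documents do not say whether anyone is masked, and section 7.3 mentions blinding only conditionally.

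It can also be said that no sensible analyst would carry a pre-operative score forward. Perhaps so, but section 6.2 does not exclude it, and the inclusive reading that reconciles the sentences is the one that makes it happen.

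**Conclusion.** The concern holds in two parts. The set is an unlabelled modified intention-to-treat set that omits randomised patients with no post-operative endpoint; on plausible small numbers this alone has little effect. The larger problem is that the low entry threshold combined with unrestricted LOCF admits pre-operative HHS as the 1-year primary outcome.

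With 5% of each arm affected, power for 5.8 points falls from 86% to about 65–72%. That rests on assumed values for the proportion carried, the 30 to 40 point gap and the absence of treatment effect in those patients; the direction does not depend on the exact values. Equal loss dilutes a real difference but does not create a false one. Bias between arms requires loss that differs by arm or relates to outcome differently by arm, and the documents give no figures on either. The sample size of 68 evaluable and 80 enrolled per arm is sound on its own assumptions.

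**What to change.** - **Section 6.3:** delete the complete-data condition and state that all randomised patients are analysed in the arm assigned. Estimate the 1-year HHS difference with a likelihood-based repeated-measures model on the 6-month, 1-year and 2-year HHS, with pre-operative HHS as covariate.
- **Section 6.2:** remove LOCF for the primary analysis, so that the two sections agree.
- **Patients with no post-operative HHS:** they contribute no outcome to this model, so the new wording alone does not bring them in. Report their number by arm and include them in a sensitivity analysis, for example multiple imputation from baseline under stated assumptions.
- **Further sensitivity analysis:** the comparison of observed 1-year HHS.

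The cost is SAP wording and slightly more programming. All the scores are already scheduled, so no patients or visits are added. Because the model uses 2-year HHS, the definitive 1-year estimate belongs in the final report described in section 8.2.

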## **7. DATA COLLECTION, HANDLING AND RETENTION**

### **7.1 SOURCE DOCUMENTATION REQUIREMENTS**

Source documentation for this study will be maintained to document the treatment and study course of a subject and to substantiate the integrity of the data. Source documentation will include, but not be limited to, worksheets, hospital and/or clinic or office records documenting subject visits including study and other treatments or procedures, medical history and physical examination information, laboratory and special assessments results, pharmacy records, device accountability records, and medical consultations (as applicable).

### **7.2. CASE REPORT FORMS**

Data for this clinical trial will be collected and documented on the subject Case Report Forms (CRFs) provided, which may be in paper form or in an electronic form. Authorized study site personnel will complete CRFs only. CRFs must be reviewed and signed by the Investigator or his/her designees.

Since there is a potential for errors, inaccuracies, and misinterpretation in transcribing data onto the CRFs, the following documents must be available at all times for inspection and comparison to the CRFs by the study monitor where appropriate:

- data query forms
- originals and photocopies/certified copies of all relevant records and reports
- copies of test results

### **7.3. ELECTRONIC DATA ENTRY**

When using electronic trial data handling and/or remote electronic trial data systems, the Sponsor should:

- Ensure and document that the electronic data processing system(s) conforms to the Sponsor's established requirements for completeness, accuracy, reliability, and consistent intended performance (i.e. validation).
- Maintain SOPs for using these systems.
- Ensure that the systems are designed to permit data changes in such a way that the data changes are documented and that there is no deletion of entered data (i.e. maintain an audit trail, data trail, edit trail).
- Maintain a security system that prevents unauthorized access to the data.
- Maintain a list of the individuals who are authorized to make data changes (see 4.1.5 and 4.9.3).
- Maintain adequate backup of the data.
- Safeguard the blinding, if any (e.g. maintain the blinding during data entry and processing).

### **7.4. STUDY DOCUMENT RETENTION**

Study documents should be retained after the study is complete as required by local, state, national, or international health authorities. IRB shall store all documents required to be stored under relevant law and IRB policy without charge. After such period, IRB may charge a reasonable and customary storage fee if Sponsor requests that IRB continue to store documents related to the Study.

